4.2.5.5 Objective Response Rate Definition and Derivations

ORR will be defined as the percentage of participants with measurable disease who have a cCR (defined as disappearance of the target PN, confirmed by a consecutive scan within 3 to 6 months after the first response (± 1 week) with no missed or non-evaluable visits as per assessment schedule, see Section 4.2.5.2) or cPR (defined as a target PN volume decrease $\geq 20\%$ compared to baseline, confirmed by a consecutive scan within 3 to 6 months after the first response, see Section 4.2.5.2) as determined by ICR per REiNS criteria.

The confirmation by a consecutive scan within 3 to 6 months (± 1 week) will be derived as CR/PR achieved on consecutive visit with no missed or non-evaluable visits as per assessment schedule.

Any cCR or cPR that occurred after a subsequent NF1-PN treatment (following study intervention discontinuation) will not be included in the numerator for the ORR calculation. Participants with no post-baseline MRI assessments will be considered as non-responders (not having a cCR or cPR).

4.2.5.6 Best Objective Response Definition

BOR will be calculated based on the overall visit responses from each MRI assessment as described in Section 4.2.5.4. It is the best response a participant has had following the start of intervention but prior to starting any subsequent NF1-PN therapy and up to and including progression or the last evaluable MRI assessment in the absence of progression. Categorisation of BOR will be based on REiNS using the following response categories: cCR, CR, cPR, PR, SD, PD, and NE.

The different ways of achieving a BOR of cCR, CR, cPR, or PR are shown in Table 8.

Table 8 BOR Categories

Post-baseline visit N	Post-baseline visit N+1	BOR
PR	PR/CR	cPR
PR	SD/PD/NE	Unconfirmed PR
CR	CR	cCR
CR	PR/SD/PD/NE	Unconfirmed CR
PR/SD/NE	CR	Unconfirmed CR
SD/NE	PR	Unconfirmed PR
NE	NE	NE

BOR, best objective response; c Confirmed; CR, complete response; NE, not evaluable; PD, progressive disease; PR, partial response; SD, stable disease.

Best objective response will be determined programmatically based on REiNS from the overall visit response using all data up until the first progression event or the last evaluable MRI assessment in the absence of progression. Best objective response will be derived using data whilst on-treatment MRI (see Section 3.3.3). The denominators will be consistent with those used in the ORR analysis.

Participants with no post-baseline MRI assessments will be considered as non-responders. For participants whose progression event is death, BOR will be calculated based on all evaluable MRI assessments prior to death using data whilst on-treatment MRI (see Section 3.3.3).

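### SAP Table 8 gives a PR followed by a CR two different BOR categories, with no stated ranking to choose between them, so the BOR table may not agree with the ORR

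*SAP*

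**What the plan says.** SAP Section 4.2.5.6 defines BOR in three steps.

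- **Principle:** "It is the best response a participant has had following the start of intervention".
- **Categories:** "Categorisation of BOR will be based on REiNS using the following response categories: cCR, CR, cPR, PR, SD, PD, and NE". Since cCR is listed separately, plain CR in this list can only be the unconfirmed CR.
- **Mapping from pairs of consecutive visits:** "The different ways of achieving a BOR of cCR, CR, cPR, or PR are shown in Table 8". Row 1 assigns PR followed by PR or CR to cPR. Row 5 reads "PR/SD/NE CR Unconfirmed CR" (first visit, next visit, BOR).

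The assignment is left to a program: "Best objective response will be determined programmatically based on REiNS from the overall visit response".

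The ORR has its own confirmation rule in SAP Section 4.2.5.5. Confirmation "will be derived as CR/PR achieved on consecutive visit with no missed or non-evaluable visits". BOR is reported under SAP Section 4.2.5.9 as a supplementary summary by cohort and total.

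**The concern.** A program needs one answer for each input, and Table 8 gives two for PR followed by CR. Without a stated ranking, the programmer must choose. The nearest guide is the printed list, in which plain CR stands ahead of cPR. Anyone who reads that list as the order of merit will tabulate a confirmed responder as unconfirmed.

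What is at stake is the agreement between two displays of the same scans. The ORR would count the child as a confirmed responder and the BOR table would not. A reader who adds cCR and cPR could get fewer responders than the ORR numerator, with no explanation in the SAP. The children affected would be those whose tumour disappeared after a partial response, which is the deepest response on the scale.

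**Working it through.** There is no planned figure to reproduce; this is a logic check on the current table.

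**1. Visit pairs.** Five visit responses (CR, PR, SD, PD, NE) give 5 × 5 = 25 ordered pairs. Each was run through the seven rows of Table 8. Exactly one pair matches two rows: PR then CR, which is cPR by row 1 and unconfirmed CR by row 5.

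**2. Is that pair confirmed for the ORR?** A CR is disappearance of the target PN, so it also satisfies the requirement of at least a 20% decrease from baseline. Scheduled scans are 16 or 24 weeks apart (SAP Section 4.2.5.1): 16 × 7 / 30.4 = 3.7 months and 24 × 7 / 30.4 = 5.5 months. Both lie inside the 3 to 6 month window. Two consecutive scheduled scans reading PR then CR therefore make a confirmed responder.

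**3. Sequences under the two possible rankings.** Here uCR is unconfirmed CR.

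| Scans | Categories matched | Printed order as ranking | cPR above uCR | ORR |
|---|---|---|---|---|
| PR, CR | cPR, uCR | uCR | cPR | responder |
| PR, PR, CR | cPR, cPR, uCR | uCR | cPR | responder |
| PR, CR, CR | cPR, uCR, cCR | cCR | cCR | responder |
| PR, CR, NE | cPR, uCR, uCR | uCR | cPR | responder |

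The result depends on the ranking, except where the CR is itself confirmed.

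**4. Is one edit enough?** Deleting PR from row 5 makes PR, CR map to cPR only. It does not cure PR, CR, NE under the printed order, because row 4 still gives uCR for CR then NE. The ranking has to be stated as well.

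**5. Coverage of the schedule.** Sequences were enumerated over the five scheduled post-baseline scans (Cycles 5, 9, 13, 19 and 25), stopping at first PD and treating any regrowth after a CR as PD. Of these, 281 patterns meet the consecutive-visit rule. Under the printed order 78 of the 281 get an unconfirmed BOR; with cPR ranked above uCR, none do. These are counts of possible patterns, not of expected children.

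**6. Size.** Protocol Section 6.1.2 gives approximately 10 evaluable participants as the minimum per cohort. One child is then 1/10 = 10 percentage points of a BOR row, and less in a larger cohort. Actual cohort sizes are redacted.

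On frequency, Protocol Section 2.2 reports 33 confirmed PRs and an ORR of 66% in SPRINT. The denominator is not printed there, but 28 participants are given as 56%, and 28 / 0.56 = 50. Then 33 / 50 = 66%, so confirmed PRs account for the whole ORR.

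**The case against.** The strongest reply is that no protocol endpoint is touched. The ORR is the secondary endpoint, with its own derivation (SAP Section 4.2.5.5) and analysis (Section 4.2.5.7), and is not computed from BOR. PR then CR counts as a response there. BOR is supplementary, and BOR and the overall visit responses are both listed, so a mismatch would be visible. The SAP requires consistent denominators but does not say that cCR plus cPR must equal the ORR numerator. All of this stands, and it keeps the point minor.

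Three stronger readings are tempting, and the documents do not carry them.

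- **That the SAP ranks unconfirmed CR above cPR.** The category list is never called a hierarchy. With cPR ranked first, PR, PR, CR is cPR. The child could be tabulated as unconfirmed; the text does not make it certain. The double assignment itself does not depend on any ranking.
- **That row 4 downgrades confirmed responders in the same way.** Row 4 reads "CR PR/SD/PD/NE Unconfirmed CR", so CR then PR is unconfirmed. However, SAP Section 4.2.5.2 defines PD as an increase of 20% or more from baseline or, once a PR has been documented, from the best response. After a PR and then a CR, any measurable volume is an increase from zero, so the next scan is PD. Only a CR with no earlier PR, read literally, can reach CR then PR. That leaves almost nothing to correct in row 4.
- **That SPRINT bounds the frequency.** The denominator of 50 is inferred. The status counts at data cut-off sum to 28 + 2 + 15 + 3 = 48, which leaves two participants unclassified. The figures point to no confirmed CR, but they cannot exclude an unconfirmed CR, which is the category in question.

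**Conclusion.** The concern holds in a limited form. Table 8 gives two outputs for PR then CR, the SAP supplies no tie-break, and row 5 conflicts with the ORR confirmation rule for that pair. If the printed category order is adopted as the ranking, a confirmed responder is shown as unconfirmed CR, and cCR plus cPR can fall below the ORR numerator. That consequence is conditional on the ranking, which the SAP leaves open.

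The effect is confined to the supplementary BOR summary. It involves only children who reach a CR after a PR without a confirmed CR. They are probably few, because SPRINT's responders were confirmed PRs, though the documents do not allow a numerical bound. This is worth correcting because it is cheap, not because it threatens the trial's conclusions.

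**What to change.** Make three changes in SAP Section 4.2.5.6.

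1. Delete PR from the first column of row 5, so that only SD or NE followed by CR gives unconfirmed CR. PR then CR is then cPR by row 1 alone.
2. State the ranking: cCR > cPR > unconfirmed CR > unconfirmed PR > SD > PD > NE.
3. Add a programming check that cCR plus cPR in the BOR table equals the ORR numerator for the same on-treatment scans, with any difference explained. This would also bring to light the rare CR-then-PR case, so row 4 needs no edit.

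The cost is one table cell, one sentence and one check, made before BOR is programmed for DCO2. No data collection, endpoint or ORR analysis changes.

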4.2.5.7 Primary Analysis of the Secondary Endpoint

ORR will be presented with corresponding 2-sided exact 95% CI based on the Clopper Pearson method (Clopper and Pearson 1934) by cohort, total in global, total in Japan and total in study.

ORR will be derived using data whilst on-treatment MRI (see Section 3.3.3).

Data will be summarised and analysed using the safety analysis set.

4.2.5.8 Sensitivity Analyses of the Secondary Endpoint

Not applicable.

4.2.5.9 Supplementary Analyses of the Secondary Endpoint

The following supplementary analyses will be presented as follows:

- Same analyses as described in the above section will be done on data using all MRI scans (regardless of treatment discontinuation but excluding MRI scans after starting subsequent NF1-PN treatment [if applicable]).
- Changes in target PN volume (absolute and percentage change from baseline) over time by cohort and total. The average from the two ICR volume assessments will be used in the analysis as tumour volume. Corresponding box plots will be presented. All PN volume data will be listed, including the two ICR volume and the average.
- BOR will be calculated based on the overall visit responses from each MRI assessment. BOR is the best response a participant has had following the start of intervention but prior to starting any subsequent therapy and up to and including progression or the last evaluable MRI in the absence of progression. BOR will be summarised by cohort and total. BOR and the overall visit response will be listed, including the ICR and investigator visit response.
- Best percentage change from baseline will be derived using the best evaluable on-treatment MRI assessment and will be summarised by cohort and total. A corresponding waterfall plot will be presented.

4.2.6 **CCI**

4.2.6.1 Definition

For the subset of participants who have a **CCI** [REDACTED], **CCI** will be defined as the **CCI**

[REDACTED], as determined by ICR per REiNS criteria.

The **CCI** [REDACTED] should coincide with the **CCI** [REDACTED] endpoint (see Section 4.2.7). The date of the **CCI** [REDACTED] will be defined as the **CCI** [REDACTED].

4.2.6.2 Derivations and Censoring Rules

If a participant **CCI**, then their **CCI** will use the **CCI** **CCI** Section 4.2.7.2). The derivation formula for **CCI** is **CCI** **CCI** will be derived based on the actual MRI assessment dates and not visit dates.

4.2.6.3 Primary Analysis of **CCI**

A **CCI** of **CCI** by cohort and total will be presented including a **CCI** table. **CCI** will also be calculated using the **CCI** and presented in a summary table by cohort and total. The percentage **CCI** at 4, 8, and 12 months and every 6 months thereafter will be summarised based on the **CCI**.

Only participants who have a **CCI** will be included in this analysis.

Swimmer plots that clearly show the profile of each participant who **CCI** by cohort will also be produced. Additional graphical symbols to depict the **CCI**, **CCI** will be added. On treatment will be designated with a different colour than post-treatment.

CCI will be derived using data whilst on-treatment MRI (see Section 3.3.3). Data will be summarised and analysed using the safety analysis set.

4.2.6.4 Additional Analyses of **CCI**

Same analyses as described in the above section will be done on data using all MRI scans (regardless of treatment discontinuation but excluding MRI scans after starting subsequent NF1-PN treatment [if applicable]).

4.2.7 **CCI**

4.2.7.1 Definition

CCI will be defined as the **CCI** (by ICR per REiNS criteria) of **CCI** **CCI** is defined in Section 4.2.5.2. The **CCI** of existing clinically relevant non-target PN is also considered **CCI** as described in Section 4.2.5.3.

4.2.7.2 Derivations and Censoring Rules

Participants who **CCI** at the time of analysis will be **CCI**. However, if the participant **CCI**, the participant will be **CCI**. The details of censoring rules are listed in Table 8.

The derivation formula for **CCI** is **CCI**

[REDACTED].

If the participant has no evaluable MRI assessments post-baseline, they will be censored at Cycle 1 Day 1 unless they die within two cycles from baseline. The **CCI** time will be derived based on actual MRI assessment dates and not visit dates.

Table 9 Summary of Censoring Guidelines for CCI

Assessment	Date of event, Death or Censoring	PFS Outcome
CCI [REDACTED]	CCI [REDACTED]	CCI [REDACTED]
CCI [REDACTED]	CCI [REDACTED]	CCI [REDACTED]
CCI [REDACTED]	CCI [REDACTED]	CCI [REDACTED]
No evaluable MRI assessment or no baseline data and no death within two cycles from baseline	Cycle 1 Day 1	Censored

MRI, magnetic resonance imaging; **CCI** [REDACTED].

Based on the scheduled visit assessment scheme (ie, every 4 cycles until Cycle 13 and every 6 cycles from then onwards), the definition of 2 missed MRI assessments will change over time and is calculated as the protocolled time between 2 subsequent scans + the protocol-allowed visit window for an early visit at the previous assessment + the protocolallowed visit window for a late visit at the expected assessment (see [Table 10](#)).

Table 10 Two Missed Visits Window Rule

Scheduled assessments	Previous REiNS assessment	Two missed MRI assessments window
Q16w \pm 1 week up to Week 48	Up to Week 15 (<Day 106)	33 weeks (231 days)
	Weeks 15 to 31 \geq 106 to \leq 217	34 weeks (238 days)
	Weeks 31 to 47 \geq 218 to \leq 329	42 weeks (294 days)
Q 24w \pm 1 week	Week 47 \geq 330	50 weeks (350 days)

MRI, magnetic resonance imaging; Q16W, every 16 weeks; Q24W, every 24 weeks; REiNS, Response Evaluation in Neurofibromatosis and Schwannomatosis.

4.2.7.3 Primary Analysis of CCI

A CCI of CCI will be presented including a CCI table by cohort and total. CCI will also be calculated using the CCI and presented in a summary table by cohort and total. The percentage CCI at 4, 8, and 12 months and every 6 months thereafter will be summarised based on the CCI .

CCI will be derived using data whilst on-treatment MRI (see Section 3.3.3). Data will be summarised and analysed using the safety analysis set.

4.2.7.4 Additional Analyses of CCI

Same analyses as described in the above section will be done on data using all MRI scans (regardless of treatment discontinuation but excluding MRI scans after starting subsequent NF1-PN treatment [if applicable]).

4.2.8 CCI

4.2.8.1 Definition

CCI will be defined as the CCI by ICR per the REiNS criteria.

4.2.8.2 Derivations and Censoring Rules

Participants who CCI at the time of analysis will be censored at their last evaluable MRI assessment. However, if the participant CCI after two or more missed cycles, the participant will be censored at the latest evaluable MRI assessment. Refer to Section 4.2.7.2 for further details on the derivation of two or more missed cycles.

The derivation formula for CCI is CCI .

If the participant has no evaluable MRI assessments post-baseline, they will be censored at Cycle 1 Day 1. The CCI will always be derived based on actual MRI assessment dates and not visit dates.

4.2.8.3 Primary Analysis of CCI

A CCI will be presented including a CCI table by cohort and total. CCI will also be calculated using the CCI and presented in a summary table by cohort and total. The percentage CCI at 4, 8, and 12 months and every 6 months thereafter will be summarised based on the CCI .

CCI will be derived using data whilst on-treatment MRI (see Section 3.3.3). Data will be summarised and analysed using the safety analysis set.

4.2.8.4 Additional Analyses of CCI

Same analyses as described in the above section will be done on data using all MRI scans (regardless of treatment discontinuation but excluding MRI scans after starting subsequent NF1-PN treatment [if applicable]).

4.2.9 CCI

4.2.9.1 Definition

CCI will be defined as the CCI

(Section 4.2.6).

4.2.9.2 Derivations

The CCI will always be derived based on the actual MRI assessment dates and not visit dates.

Only participants who have CCI will be evaluated for CCI.

The derivation formula for CCI is CCI

4.2.9.3 Primary Analysis of CCI

A CCI of CCI will be presented including a CCI table by cohort and total. CCI will also be calculated using the CCI and presented in a summary table by cohort and total. The percentage CCI at 4, 8, and 12 months and every 6 months thereafter will be summarised based on the CCI .

CCI will be derived using data whilst on-treatment MRI (see Section 3.3.3). Data will be summarised and analysed using the safety analysis set.

4.2.9.4 Additional Analyses of CCI

Same analyses as described in the above section will be done on data using all MRI scans (regardless of treatment discontinuation but excluding MRI scans after starting subsequent NF1-PN treatment [if applicable]).

4.2.10 CCI

4.2.10.1 Definition

CCI will be measured using the CCI . The CCI will be used for participants who are aged CCI years at the time of the assessment, and the CCI will be used for participants who are aged CCI years at the time of the assessment. In this study, CCI will be used.

The [REDACTED] CCI [REDACTED] Scales for participants aged [REDACTED] years consist of [REDACTED]
[REDACTED]

The [REDACTED] CCI [REDACTED] Scales for participants aged [REDACTED] years consist of [REDACTED]
[REDACTED]

A copy of the [REDACTED] CCI [REDACTED] is provided in CSP Appendix J 5. The [REDACTED] CCI [REDACTED] questionnaire will be performed at visits specified in the CSP.

4.2.10.2 Derivations

Each item is scored on a [REDACTED] CCI [REDACTED]

The [REDACTED] CCI [REDACTED] report items are reverse-scored and linearly transformed to a [REDACTED] CCI [REDACTED] so that higher scores indicate better [REDACTED] CCI [REDACTED]. Subscale scores are computed as the sum of the items divided by the number of items answered (this accounts for missing data). A Total Scale Score will also be derived as the sum of all the items divided by the number of items answered on all the scales. If more than 50% of the items in the scale are missing, the scale score is not computed.

The [REDACTED] CCI [REDACTED] will be further pooled into the [REDACTED] CCI [REDACTED]
[REDACTED];
[REDACTED] CCI [REDACTED]
[REDACTED] CCI [REDACTED]

At each post-baseline assessment, the absolute change in [REDACTED] CCI [REDACTED] scores from baseline will be calculated as the post-baseline value minus baseline value for each item, [REDACTED] CCI [REDACTED], [REDACTED] CCI [REDACTED]

The change from baseline values in the [REDACTED] CCI [REDACTED], [REDACTED] CCI [REDACTED], [REDACTED] CCI [REDACTED] will be classified as improvement/no

change/deterioration compared to baseline scores at each scheduled visit using the CMT reported in the literature (CCI [REDACTED]) as follows:

- Improvement: absolute change from baseline \geq CMT points
- Deterioration: absolute change from baseline $\leq -$ CMT points
- No change: absolute change from baseline $>$ CMT and $<$ CMT points between The CMT points differ for the CCI [REDACTED] and are relevant only for the CCI [REDACTED]. The CMTs are reported in Table 11 based on CCI [REDACTED].

Participants will be classified with impaired global CCI [REDACTED] Yes/No at each scheduled visit using the CCI [REDACTED]. Participants are classified with impaired global CCI [REDACTED] if their scores fall one standard deviation below the population sample mean as reported by CCI [REDACTED]; exact thresholds are reported in Table 11.

Table 11 PedsQL Cut-off Scores (Total Scale, Physical, and Psychosocial) Denoting At-Risk for HRQoL Impairment and Thresholds for Clinically Meaningful Changes for Parent/Guardian-report

CCI [REDACTED] scores	Cut-off CCI [REDACTED] scores indicating CCI [REDACTED] (if values fall below)	Clinically meaningful thresholds
CCI [REDACTED]	CCI [REDACTED]	CCI [REDACTED]
CCI [REDACTED]	CCI [REDACTED]	CCI [REDACTED]
CCI [REDACTED]	CCI [REDACTED]	CCI [REDACTED]

4.2.10.3 Handling of Missing Data

If more than 50% of the items in the scale are missing, the CCI [REDACTED] is not computed. If any of the subscales are missing for the CCI [REDACTED], then it will not be calculated.

4.2.10.4 Analysis of CCI

All analyses of the CCI [REDACTED] will be based on the transformed scores only. Summary statistics will be presented by cohort and total.

Summaries for cumulative participant disposition and compliance over time (defined in Section 3.3.9 and 3.3.10, respectively) by each scheduled visit will be reported.

For the CCI [REDACTED]

CCI, all age groups can be analysed together. For the CCI [REDACTED], the age groups CCI [REDACTED] () can be analysed together, while the CCI [REDACTED] for age group CCI [REDACTED] years needs to be analysed separately.

CCI [REDACTED]

A summary table with descriptive statistics for the absolute values and change from baseline in the CCI [REDACTED] will be presented for each scheduled visit by age group [REDACTED] [REDACTED].

CCI [REDACTED]

A summary table with descriptive statistics for the absolute values and change from baseline in the CCI [REDACTED] will be presented for each scheduled visit.

Mean absolute values and change from baseline in the CCI [REDACTED] will be plotted over time.

Counts and percentages for impaired global CCI [REDACTED] in the CCI [REDACTED] will be provided for each scheduled visit.

Counts and percentages for category improvement/no change/deterioration for CCI [REDACTED], CCI [REDACTED] at each scheduled visit will be provided.

Change from baseline in the CCI [REDACTED] will be analysed using a REML-based MMRM analysis. The analysis will be based on observed data (ie, data collected at each time point without carrying forward previous values). As drop out will accumulate during the study, the proportion of available data may become too small for adequately estimating the statistical model. Therefore, the first visit where less than CCI [REDACTED] participants have non-missing data will be used as a cut-off point, and only visits prior to that time point will be included in the model.

The response variable will be the change from baseline to each post-baseline scheduled visit. The model will include terms for scheduled visit, baseline CCI [REDACTED] score, cohort, cohort-by-scheduled visit interaction, and baseline-by-scheduled visit interaction. The model will present least square mean estimates estimated on the cohort-by-scheduled visit interaction, standard errors, 95% CIs, and p-values for mean changes from baseline to each scheduled visit.

The analysis will be conducted using PROC MIXED in SAS. Missing data will be modelled through direct likelihood techniques, which use the information from the observed data via the within-patient correlation structure (covariance matrix) to provide

information about the unobserved outcomes. An unstructured covariance matrix will be used to model the within-patient correlations between the repeated measurements.

If the fit of the unstructured covariance structure fails to converge, every attempt should be made to ensure convergence is obtained from the unstructured correlation structure.

Parameters will be tried to be estimated by means of the Fisher's scoring algorithm rather than the default Newton-Raphson algorithm. If convergence is still not reached after the change in estimation algorithm, a more parsimonious model will be implemented using one of the following structured covariance structures in order until convergence is reached: first-order autoregressive and compound symmetry. The Kenward-Roger approximation will be used to estimate denominator degrees of freedom. The unique participant identifier will also be included as a class variable. A REPEATED statement over the visits will be included with the unique participant identifier as the SUBJECT variable in the REPEATED statement.

All CCI data (both the raw and transformed scores) will be fully listed, including individual items, CCI and change from baseline.

Data will be summarised and analysed using the safety analysis set.

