Section 4..2.10.4	29Apr2024	Clarification that MMRM has cohort as fixed factor with estimates on the on the cohort-by-scheduled visit interaction and model not run by cohort	N/A	Clarification on modelling
Section 4.3 Pharmacodynamic Endpoint(s)	29Apr2024	PD analysis will not be performed in CSR.	N/A	PD data were not collected.
Section 4.4.1	29Apr2024	Added derivation of dose by BSA normalised (DBN)	N/A	Requested by PK scientist to help data interpretation in CSR
Section 4.4.2.1 Plasma Concentrations Section 4.4.2.2 Plasma parameters	29Apr2024	Remove cohorts and show the table only for the total by BSA.	Yes	Due to the most of the BSA groups within each cohort have less than 3 participants, PK analysis by BSA groups will be only undertaken in the total global.

Section 4.6.1 Exposure and treatment compliance	29Apr2024	Update text for Duration of exposure calculation adding date of DCO. Transition to capsule formulation information will be listed in the exposure listing.	N/A	Provide clarity and consistency in the Duration of exposure calculation. Transition to capsule formulation information will be listed in the exposure listing.
Section 4.6.2 Adverse Event	29Apr2024	Added granule formulation flag to the AEs listings.	Yes	Provided detailed information about the formulation (granule or

CATEGORY Change refers to:	Date	Description of change	In line with CSP?	Rationale
		Added table for AESI		capsule) when the AE starts. Provided terms to be mapped as AESI
Section 4.6.12 Physical Examination Including CCI	29Apr2024	Remove summary tables for Physical Examination	Yes	Not necessary, data for Physical Examination are available in listings section. Besides any abnormal or significant event will be collected in AEs section.

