4.2.11.3 Analysis of CCI

Summaries for cumulative participant disposition and compliance over time (defined in Section 3.3.9 and 3.3.10, respectively) by each scheduled visit will be reported. Summary statistics will be presented by cohort and total.

A summary table with descriptive statistics for the absolute values and change from baseline in the weekly average total score will be presented for each scheduled visit.

Counts and percentages for each change from baseline category for the weekly average total score at each scheduled visit will be provided.

Counts and percentages for category improvement/no change/deterioration for the weekly average total score at each scheduled visit will be provided.

Change from baseline in the weekly average total scores will be analysed using a REML-based MMRM (as described in Section 4.2.10.4). usingWithin each cohort, the corresponding baseline value rather than baseline CCI score will be used.

Counts and percentages for CCI at each scheduled visit will be provided.

All CCI data will be fully listed, including individual items, total scores, and weekly averages.

Data will be summarised and analysed using the safety analysis set.

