4.2.12.3 Analysis of CCI

Summaries for cumulative participant disposition and compliance over time (defined in Section 3.3.9 and 3.3.10, respectively) by each scheduled visit will be reported. Summary statistics will be presented by cohort and total.

A summary table with descriptive statistics for the absolute values and change from baseline in the weekly average total score will be presented for each scheduled visit.

Counts and percentages for each change from baseline category for the weekly average total score at each scheduled visit will be provided.

Counts and percentages for category improvement/no change/deterioration for the weekly average total score at each scheduled visit will be provided.

Change from baseline in the weekly averages will be analysed using a REML-based MMRM (as described in Section 4.2.10.4), and considering CCI score at baseline rather than baseline CCI score.

Counts and percentages for CCI [REDACTED] at each scheduled visit will be provided.

All CCI [REDACTED] data will be fully listed, including individual scores and change from baseline.

Data will be summarised and analysed using the safety analysis set.

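### The MMRM reports baseline-adjusted LS means as each cohort's mean change from baseline, so the exploratory CIs and p-values answer a different question from the one on their label

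*SAP*

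**What the plan says.** SAP 4.2.10.4 defines the outcome of the repeated-measures model: "The response variable will be the change from baseline to each post-baseline scheduled visit". Besides scheduled visit, the terms are the baseline "score, cohort, cohort-by-scheduled visit interaction, and baseline-by-scheduled visit interaction". There is no cohort-by-baseline term, so each visit has one baseline slope shared by all cohorts. The SAP Amendment History (entry of 29Apr2024 for this section) confirms a single joint model with cohort as a fixed factor, with estimates taken on the "cohort-by-scheduled visit interaction and model not run by cohort".

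The section asks for "least square mean estimates estimated on the cohort-by-scheduled visit interaction, standard errors, 95% CIs, and p-values for mean changes from baseline" to each scheduled visit. It names PROC MIXED, an unstructured covariance and Kenward-Roger degrees of freedom. It does not say at which baseline value the LS means are evaluated.

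Two later sections reuse the model. SAP 4.2.12.3 substitutes its own "score at baseline rather than baseline CCI score". SAP 4.2.11.3 says "the corresponding baseline value rather than baseline CCI score will be used", but that clause opens with a run-together reference to working within each cohort, so the intended baseline handling is unclear.

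Under SAP 1.1, Cohort 1 is aged 4 to under 7 years and Cohort 2 is aged 1 to under 4 years, both outside Japan. The Japan Cohort spans 1 to under 7 years. Nothing is randomised.

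**The concern.** The label promises each cohort's mean change from baseline. An LS mean from a model with a baseline covariate is that change moved to a chosen baseline value. Moving groups to a common baseline helps a between-group contrast, but 4.2.10.4 specifies none; it reports within-cohort changes only.

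Two things follow if the default evaluation point is used. The estimate shifts by slope × (pooled minus cohort mean baseline). The SE also leaves out the sampling variation of the baseline mean. Under regression to the mean the slope of change on baseline is negative, so the cohort with the better baseline shows the larger apparent improvement, whichever way the scale runs.

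These are the only p-values the SAP specifies. The same section tabulates descriptive change from baseline, with summaries by cohort. The report could therefore show two different figures under one description, with the p-value on the shifted one. An apparent difference between age groups could come from the adjustment point alone.

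**Working it through.** **Inputs.** From the SAP: the response, model terms, joint fit and 95% CIs. I take the tests as two-sided at 5%. The documents give no baseline means, SDs, correlations or usable cohort sizes. Assumed: Cohort 1/Cohort 2/Japan of 15/15/5, 20/10/5 or 10/20/5; equal SD of 1 at both times; pre-post correlation r from 0.3 to 0.7; Japan midway between the Global Cohorts at baseline; complete normal data; true mean change zero in every cohort.

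**Formula.** With complete data and an unstructured covariance, the MMRM at a visit equals an ANCOVA of change on cohort and baseline:

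- LSmean_c = mean change_c + b(x̄_pooled − x̄_c), where b has expectation r − 1
- reported SE² = s²[1/n_c + (x̄_pooled − x̄_c)²/Sxx], with s² estimating 1 − r²

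**Nominal level first.** Against the model's own null (zero change at the pooled baseline), simulation rejects 4.7% to 5.2%. The 95% intervals are right for that quantity.

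**Equal baselines, cohort's own null.** The true variance of the LS mean is about (1 − r²)/n_c + (1 − r)²/N, but the SE reflects only the first term. With n_c = 15 and N = 35:

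- r = 0.3: 0.0607/(0.0607 + 0.0140) = 0.81; P(|Z| > 1.96√0.81) ≈ 7.7%
- r = 0.5: 0.0500/(0.0500 + 0.0071) = 0.875; about 6.7%
- r = 0.7: 0.0340/(0.0340 + 0.0026) = 0.93; about 5.9%

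Simulation at 15/15/5 agrees: about 6-8%. Across the three splits it is 5-9%.

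**Unequal baselines.** Take 15/15/5, r = 0.5 and a gap of 0.8 SD. The pooled mean lies 0.4 SD from each Global Cohort, so the shift is (1 − 0.5) × 0.4 = 0.20 SD, in opposite directions. The mean reported SE is 0.233 and the true SD of the estimate about 0.245. With 31 df the critical distance is 2.04 × 0.233 = 0.475. Then P(Z > (0.475 − 0.20)/0.245) + P(Z < −(0.475 + 0.20)/0.245) ≈ 13%. Simulation gives about 14%.

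Simulated rejection in the Global Cohorts over the three splits:

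| Baseline gap | r = 0.3 | r = 0.5 | r = 0.7 |
|---|---|---|---|
| 0.5 SD | 12-14% | 9-10% | 7-8% |
| 0.8 SD | 18-21% | 13-16% | 9-11% |
| 1.0 SD | 22-29% | 16-20% | 10-13% |

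The 29% comes from an uneven split; at 15/15/5 the largest value is about 27%. The unadjusted cohort mean change rejects 4-6% throughout.

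**Cohort's own mean baseline.** The shift vanishes, but the reported variance (1 − r²)/n_c faces a true variance of 2(1 − r)/n_c. The ratio is (1 + r)/2, that is 0.65, 0.75 or 0.85. Large-sample rejection is P(|Z| > 1.96√ratio) = 11.4%, 9.0% or 7.1%. Simulation gives about 6-12%.

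**Effect on a real change.** With a true change of 0.6 SD in every cohort (15/15/5, r = 0.5, gap 0.8 SD), the LS means average 0.80 SD in one Global Cohort and 0.40 SD in the other, with power 90% and 39%. The unadjusted contrast has about 62% in both.

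**The case against.** The strongest reply is that this is a labelling mismatch and not a faulty test. That is right as far as it goes: the model holds its level for the null it tests. The SAP, however, describes another quantity, and no choice of baseline value makes the reported SE fit that description.

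A reader might infer that the SAP instructs evaluation at the pooled baseline. It does not; that is a software default filling a silence. The within-cohort wording in 4.2.11.3 could even point to cohort-specific handling, although the Amendment History says the model is not run by cohort.

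A reader might also infer a fixed multiple of the nominal error, such as two to five times. The documents do not support one. With equal baselines the excess is small, and two-fold inflation at 15 per Global Cohort needs a gap of about 0.5 SD at r = 0.5, or 0.8 SD or more at r = 0.7. Age-defined cohorts make a gap plausible but do not establish one.

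Nor does the plan promise a total from this model: the by-cohort-and-total statement in 4.2.10.4 concerns summary statistics.

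The stakes are limited. The endpoints are exploratory, CSP 9.1 disclaims formal hypotheses, and the endpoint table in SAP 4.2 lists LS means and CIs for these analyses without p-values. Unadjusted changes are already tabulated, though 4.2.10.4 attaches the model's CI and p-value to the LS means.

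Carry-over to the other two instruments is not shown. Both depend on redacted age limits and ability to respond, so one Global Cohort may contribute few or no children.

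**Conclusion.** The point holds as a mismatch between the quantity named and the quantity estimated, with CIs and p-values that do not fit the name. If the default evaluation point is used, rejection of zero mean change in a Global Cohort at nominal 5% is about 6-8% with equal baselines. It is about 7-29% over assumed gaps of 0.5 to 1.0 SD and correlations of 0.3 to 0.7. Using each cohort's own mean baseline leaves about 6-12%. All these figures rest on assumed sizes of around 15/15/5, complete normal data and equal variances. The consequence is confined to interpreting exploratory CIs and p-values; no primary or secondary conclusion depends on them. It should still be corrected before these outcomes are analysed at DCO2, because the remedy needs no new data.

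**What to change.** In SAP 4.2.10.4, for the within-cohort changes, model the score itself at all visits with baseline as one of the repeated responses. Use terms for visit, cohort and cohort-by-visit, keeping the unstructured covariance and Kenward-Roger. Report each cohort's visit-minus-baseline contrast and attach the 95% CI and p-value to it. Missing visits are still handled by likelihood, because baseline informs later visits through the covariance matrix. A simpler alternative is the unadjusted cohort mean change with its CI.

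If the baseline-adjusted LS means are kept, state the baseline value used and label them as the change at that common baseline.

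Apply the same change in 4.2.11.3 and 4.2.12.3 where more than one cohort contributes data, and rewrite the garbled clause in 4.2.11.3.

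The cost is SAP wording and a small code change. CIs will be somewhat wider, and the unstructured matrix gains one dimension in a small sample. The convergence fallback in 4.2.10.4 must therefore cover the larger matrix. It should also recognise that under first-order autoregressive or compound symmetry the contrast's SE depends directly on the assumed baseline-to-visit correlation.
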